7.4. Unscheduled Visits

Unscheduled visits should be performed whenever necessary, i.e. in case of adverse events or in case of symptoms of clinical disease progression. Evaluations and/or assessments will be performed, as deemed appropriate by the investigator based on the nature of the event. Results will be documented in the patient's file and recorded in the CRF. If a patient is withdrawn from the study, efforts should be taken to perform all examinations scheduled for the End-of-Core-Study visit (please see section 7.5.1, 30-day Safety Follow-up Visit).

7.5. In Case of Adverse Events

The following procedures and assessments will be performed in the case of an unscheduled visit resulting from an adverse event:

- Physical examination
- Vital signs/temperature
- Routine bloods, U/E, LFTs, LDH, Coagulations screen, FBC

In case of neurological adverse events leading to treatment interruption/discontinuation or dose reduction, the following additional assessments should be performed:

- Cranial MRI
- Assessment of cerebrospinal fluid, if appropriate

7.6. Laboratory procedures

All laboratory samples collected, including urine, blood and bone marrow, will be processed using routine standard of care procedures. All assessments are performed at Guy's Hospital with no requirement for shipment or analysis at other institutions.

All blood and bone marrow samples collected would be considered standard of care for a patient being treated for AML. These samples will be used for research purposes in the study.

8. Assessment of Efficacy

8.1. Definitions for Treatment Response Evaluation

- Complete molecular response is achieved if there is no amplification of *RUNX1-RUNX1T1* fusion transcripts in a technically adequate sample obtained after the first cycle of treatment.
- Two weeks after the first post treatment bone marrow sample was obtained (which is expected to be identical with day 1 of the second cycle), another bone marrow aspiration has to be obtained in case the previous specimen was technically suboptimal and did not allow evaluation for molecular complete response.
- Molecular relapse is defined as re-appearance of *RUNX1-RUNX1T1* fusion transcripts on two consecutive samples with an increase in transcript expression of

- more than 1 log₁₀ in a patient who previously tested negative in at least two technically adequate samples
- Molecular progression is defined as an increase in disease-related transcript expression levels of more than 1 log₁₀ confirmed on a second consecutive sample.
- Haematological relapse is defined as unequivocal detection of > 5% leukaemia cells in bone marrow as measured by cytological, microscopic assessment, presence of circulating leukaemia blasts, or extramedullary leukaemia.

8.2. Procedures for Assessing Efficacy Parameters

RT-qPCR analysis on the bone marrow aspirate performed on day 29 of cycle 1 will be used to assess the primary endpoint. Verification of receipt of a sufficient sample by the central MRD lab is a rate limiting step for determination of eligibility and potential protocol treatment.

Procedures for assessment of secondary endpoints will include

- Regular and unscheduled clinical assessments for AEs/SAEs as outlined in section 7
- RT-qPCR on bone marrow aspirates performed at the end of each treatment cycle
- Follow-up assessments (refer to section 7.3) to assess for relapse and survival
- Review of CRFs and patient medical notes to assess days of hospital admission, antibiotic and antifungal use and blood component transfusions

8.3. Bone Marrow Aspiration

Evaluation of MRD will be performed on bone marrow aspirate samples. Each bone marrow will be evaluated for presence of leukaemia cells with differential count by light microscopy at the local laboratory and results entered on the CRF.

At the end of the first treatment cycle (D29) a bone marrow aspiration will be performed and shipped to the central MRD laboratory for the evaluation of the primary endpoint. In case of technically suboptimal samples (i.e. *ABL* Ct >26), a second bone marrow aspiration will be performed to confirm whether the primary endpoint of complete molecular response was reached or not.

At the end of each treatment cycle (D29) and during the efficacy follow-up visits a bone marrow aspiration will be performed to evaluate MRD and morphology defining the percentage of leukemic blasts in bone marrow. Furthermore, in the event of abnormal blood counts (suggesting leukemic relapse), a bone marrow evaluation should be performed prior to initiating the subsequent cycle of treatment with blinatumomab.

Additional tests conducted by the investigators but not required by protocol such as immunophenotypic, cytogenetic or molecular analyses during the study will be collected and documented in the CRF. During the study, haematological/morphological assessments of the bone marrow will be performed locally.

9. Assessment of Safety

Adverse events (AEs) will be reported from the time of consent up to ninety days after the completion of the final dose of Blinatumomab.

All serious adverse events (SAEs) must be reported immediately (and within 24 hours of knowledge of the event) by the PI at the participating site to the Clinical Trials Office (CTO).

9.1. Definitions

The Medicines for Human Use (Clinical Trials) Regulations 2004 and Amended Regulations 2006 gives the following definitions:

Term	Definition								
Adverse Event (AE)	Any untoward medical occurrence in a clinical trial participant administered a medicinal product, which is not necessarily caused by or related to that product.								
Adverse Reaction (AR)	Any untoward and unintended response in a clinical trial participant to an investigational medicinal product which is related to any dose administered to that participant								
Serious Adverse Event	Any adverse event that -								
(SAE)	Results in death								
	Is life-threatening*								
	 Required hospitalisation or prolongation of existing hospitalisation** 								
	Results in persistent or significant disability or incapacity								
	Consists of a congenital anomaly or birth defect								
	Other medically important condition***								
Serious Adverse Reactions (SARs)	Any SAE occurring in a clinical trial participant for which there is a reasonable possibility that it is related to the IMP at any dose administered.								
Suspected Unexpected Serious Adverse Reactions (SUSARs)	A SAR, the nature and severity of which is not consistent with the Reference Safety Information (RSI) for the IMP.								

^{*}Note: The term 'life-threatening' in the definition of serious refers to an event in which the trial participant was at risk of death at the time of the event or it is suspected that used or continued used of the product would result in the subjects death; it does not refer to an event which hypothetically might have caused death if it were more severe.

9.2. Trial Specific SAE Reporting requirements

In addition to the SAE reporting requirements above, for the purposes of this trial the following events will also be considered SAEs: Complications at the central venous catheter site like infections, thrombosis or leakage are commonly observed complications in the treatment of leukaemia patients and are to be expected in this trial. An identified complication that involves the central venous catheter, even though it does not meet the definition of a SAE is to be reported on a SAE Report Form and will be processed as a SAE. Such a device-related complication must be documented and reported to Amgen as event related to study procedure.

^{**} **Note:** Hospitalisation is defined as an inpatient admission, regardless of the length of stay, even if the hospitalisation is a precautionary measure for continued observation. Preplanned hospitalisation e.g. for pre-existing conditions which have not worsened, or elective procedures, does not constitute an SAE.

^{***} **Note:** other events that may not result in death, are not life-threatening, or do not require hospitalisation, may be considered as an SAE when, based upon appropriate medical judgement, the event may jeopardise the participant and may require medical or surgical intervention to prevent one of the outcomes listed above.

Life-threatening and fatal adverse reactions are considered unexpected for the purpose of expedited reporting.

9.3. Causality

Causal relationship will be assessed for blinatumomab (IMP) only.

The Chief Investigator (or another delegated medically qualified doctor from the trial team) will assess each SAE to determine the causal relationship:

Relationship	Description	Reasonable possibility that the SAE may have been caused by the IMP?
Unrelated	There is no evidence of any causal relationship with the trial/intervention	No
Unlikely	There is little evidence to suggest there is a causal relationship with the trial/intervention (e.g. the event did not occur within a reasonable time after administration of the trial medication). There is another reasonable explanation for the event (e.g. the participant's clinical condition, other concomitant treatment).	No
Possible	There is some evidence to suggest a causal relationship with the trial/intervention (e.g. because the event occurs within a reasonable time after administration of the trial medication). However, the influence of other factors may have contributed to the event (e.g. the participant's clinical condition, other concomitant treatments).	Yes
Probable	There is evidence to suggest a causal relationship and the influence of other factors is unlikely.	Yes
Definite	There is clear evidence to suggest a causal relationship and other possible contributing factors can be ruled out.	Yes

9.4. Expectedness

The Chief Investigator (or another delegated appropriately qualified individual) will assess each SAR to perform the assessment of expectedness.

The expectedness assessment should be made with reference to the current Reference Safety Information (RSI) for blinatumomab. Expectedness decisions must be based purely on the content of the RSI; other factors such as the participant population and participant history should not be taken into account. Expectedness is not related to what is an anticipated event within a particular disease.

SARs which add significant information on specificity or severity of a known, already documented adverse event constitute unexpected events. For example, an event more specific or more severe than that described in the RSI is considered unexpected.

9.5. Reporting procedures

Death as a result of disease progression and other events that are primary or secondary outcome measures are not considered to be SAEs and should be reported in the normal way, on the appropriate CRF.

The PI (or delegated medically qualified doctor from the trial team) should sign and date the SAE report to acknowledge that he/she has performed the seriousness and causality assessments. Investigators should also report SAEs to their own trust in accordance with local practice.

All SAEs, SARs and SUSARs (excepting those specified in this protocol as not requiring reporting) will be reported immediately (and certainly no later than 24hrs) by the Investigator to the KHP-CTO and CI for review in accordance with the current Pharmacovigilance Policy.

The participant will be identified only by trial number, date of birth and initials. The participant's name should not be used on any correspondence.

It is also required that sites respond to and clarify any queries raised on any reported SAEs and report any additional information as and when it becomes available through to the resolution of the event. Additionally, the KHP-CTO and Amgen may request additional information relating to any SAEs/SARs and the site should provide as much information as is available to them in order to resolve these queries.

Serious Adverse Event (SAE) email address:

[contact]

Adverse events should be reported from the time of signature of informed consent, throughout the treatment period up to, and including 90 days after the participant receives their last dose of the IMP. Serious adverse reactions (such as long-term side effects of trial treatment under investigation) should continue to be reported until the end of follow up.

Adverse events (AE) should be graded using the NCI Common Terminology Criteria for Adverse Events (CTCAE) Version 5.0. The toxicity grades should be recorded on the toxicity part of the CRF.

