4.3. Secondary endpoints

- Incidence of patients experiencing a grade 3 or greater non-haematological toxicity during the first cycle of treatment.
- Incidence of molecular complete remission at any time from trial entry (evaluated at end of trial)
- Molecular relapse free survival time (evaluated at end of trial)
- Overall survival time (evaluated at end of trial)
- Number of days of hospital admission at 1, 3 and 6 months from entry
- Number of days on intravenous antibiotics or antifungals at 1, 3 and 6 months
- Number of blood components infused at 1, 3 and 6 months

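### The SAE exemption in section 9.5 literally covers serious grade 3+ non-haematological toxicity in cycle 1, because that toxicity is a secondary endpoint; it contradicts sections 9, 9.1, 9.2 and 9.6

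*Protocol*

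**What the plan says.** Protocol section 9.5 opens with an exemption: "Death as a result of disease progression and other events that are primary or secondary outcome measures are not considered to be SAEs". It gives these events another route, saying that they "should be reported in the normal way, on the appropriate CRF". The expedited duty in the same section then carries the exemption forward: "All SAEs, SARs and SUSARs (excepting those specified in this protocol as not requiring reporting) will be reported immediately", with a limit of 24 hours to the clinical trials office and the chief investigator.

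The secondary endpoints in section 4.3, repeated in the synopsis, include "Incidence of patients experiencing a grade 3 or greater non-haematological toxicity during the first cycle of treatment". They also include "Number of days of hospital admission at 1, 3 and 6 months from entry" and overall survival time.

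Section 9.1, which attributes its definitions to the UK clinical trial regulations, makes an adverse event serious if, among other criteria, it "Results in death", is life-threatening, or leads to or prolongs hospitalisation. It makes no exception for events that are also endpoints.

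**The concern.** An exemption for outcome measures does little harm when every outcome is an efficacy event such as relapse. Here one of the seven secondary endpoints is a toxicity endpoint. It covers the period and the kinds of event, cytokine release and neurological effects among them, for which section 5.10 and the management table in section 21.1 ask for close observation.

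A site that follows section 9.5 as written would put a serious cycle 1 neurotoxicity on the CRF and send no SAE report. The sponsor would not hear of it within 24 hours, and nobody would be required to judge its causality or expectedness. The 7- and 15-day clocks in section 9.6 run from receipt at the trials office, so they would not start. What is at stake is prompt knowledge of serious drug reactions in a small single-arm study, and compliance with the protocol's own regulatory reporting rules.

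**Working it through.** No arithmetic applies; the check is a comparison of texts.

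**Step 1: is the event in the exempted class?** Section 9.5 exempts events that are secondary outcome measures. Section 4.3 lists grade 3+ non-haematological toxicity in cycle 1 as a secondary endpoint, and section 4.1 lists it as a secondary objective. No inference is needed, and nothing in 9.5 confines the exemption to efficacy outcomes or keeps events possibly related to blinatumomab reportable.

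**Step 2: what follows from not being an SAE?**
- Section 9.1 defines a SAR as an SAE with a reasonable possibility of a causal link, and a SUSAR as a SAR inconsistent with the reference safety information.
- Section 9.3 requires a causality assessment for each SAE.
- Section 9.4 requires an expectedness assessment for each SAR.
- Section 9.6 sets regulatory timelines for SUSARs.

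Each step takes its input from the one before. An event removed at the SAE step enters none of them.

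**Step 3: what do the other sections require?**

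| Section | Requirement | Relation to 9.5 |
|---|---|---|
| 9 (opening) | All SAEs reported within 24 hours, no exception stated | 9.5 adds an exception |
| 9.1 | Death, threat to life and hospitalisation make an event serious | Direct contradiction: the same event is serious in 9.1 and not an SAE in 9.5 |
| 9.2 | Life-threatening and fatal reactions count as unexpected for expedited reporting | Has no effect for an exempted cycle 1 toxicity |
| 9.6 | Fatal or life-threatening SUSARs within 7 days, others within 15 | Cannot be triggered for an exempted event |

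Section 9.2 also sends catheter complications that do not meet the SAE definition through the SAE process, and section 5.12 does so for overdose without symptoms. Read literally, a catheter leak is expedited while a grade 4 neurotoxicity in cycle 1 is not.

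**Step 4: how far does the exemption reach?**
- *Cycle 1 non-haematological toxicity, grade 3+:* covered directly.
- *Haematological toxicity, and toxicity in cycles 2 to 4:* not covered by the toxicity endpoint.
- *Death from progression:* exempted by name.
- *Other deaths:* unclear. Death is the event behind overall survival, but the endpoint is a survival time.
- *Admissions:* unclear. The endpoint is a count of days, and the event that causes an admission is not itself the outcome measure.

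**The case against.** The strongest reply is that the sponsor plainly did not mean this. Section 9 wants all SAEs within 24 hours, 9.2 and 9.6 provide for expediting life-threatening and fatal reactions, and 9.5 itself asks for serious adverse reactions to be reported until the end of follow-up. That is good evidence of intent, and it is why the defect is best called an internal contradiction. It does not cure the text. Section 9.5 is the specific exception, the 24-hour rule incorporates it through the words "excepting those specified in this protocol as not requiring reporting", and a reaction can be a SAR only if it is first an SAE.

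Three stronger readings are tempting, and the documents do not support them.

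- A reader might infer that all deaths and all admissions are removed from expedited reporting. Only progression death is named, and naming it would be redundant if overall survival already exempted every death. The admission endpoint is a resource count, not an event. These two limbs are ambiguous, no more.
- A reader might infer that the stage I safety evaluation would lack data. Exempted events still go on the CRF, 9.5 has toxicity grades recorded there, and section 10.2 reports AEs by patient and cycle. The grade 3+ data are kept; what is lost is speed and the causality and SUSAR assessment.
- A reader might size the problem with the 10% and 3% rates of grade 3 and 4 neurological events that section 3 cites from the ALL trial. Those rates come from another disease and up to four cycles, and grade 3 is not the same as serious. They would show how often events occur, not how often they go unreported.

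**Conclusion.** Wrong as written. On its plain wording, section 9.5 takes serious grade 3+ non-haematological toxicity in cycle 1 out of the SAE class, and so out of 24-hour reporting, causality and expectedness assessment, and SUSAR reporting. That contradicts the seriousness criteria in 9.1 and defeats the rules in 9, 9.2 and 9.6. For non-progression deaths and admissions the wording is only ambiguous.

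The size is not a number. The rule applies to every treated patient throughout cycle 1, and its consequence is late notification and missed SUSAR assessment. The conclusion rests on reading 9.5 literally, as a site might, and on the chain of definitions in 9.1. It assumes nothing about event rates and does not claim that the sponsor intended the exemption to reach this far. It should be corrected before further patients are treated under this text.

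**What to change.** Reconcile section 9.5 with 9, 9.1, 9.2 and 9.6 in one sentence. Limit the exemption to death from progression of the leukaemia and, if the sponsor wishes, to efficacy outcomes listed by name, such as relapse. State that any event meeting the seriousness criteria of 9.1, including grade 3+ toxicity and any event possibly related to blinatumomab, is reported as an SAE even when it is also an endpoint. This would also settle the position of non-progression deaths and of events leading to admission.

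The cost is one sentence by amendment and a few more SAE forms. The endpoints, the sample size and the analysis do not change.

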9.6. SUSAR reporting

Guy's and St Thomas' Hospitals NHS Trust is undertaking the duties of trial Sponsor and has delegated to the Kings Health Partners Clinical Trials Office (KHP-CTO) the responsibility for reporting SUSARs and other SARs to the regulatory authorities (MHRA and relevant ethics committees) and to Amgen as follows:

The KHP-CTO will report SUSARs to the regulatory authorities (MHRA, competent authorities of other EEA (European Economic Area) states in which the trial is taking place.

The Chief Investigator will report to the relevant ethics committee. Reporting timelines are as follows:

- SUSARs which are fatal or life-threatening must be reported to the MHRA and REC within 7 calendar days of receipt at theKHP- CTO. If report is incomplete then additional follow-up information should be reported within a further 8 calendar days of submitting the initial report.
- SUSARs that are not fatal or life-threatening must be reported to the MHRA and REC within 15 days of receipt at the KHP-CTO. Any additional, relevant information must be reported within a further 15 days.
- SUSARs will be reported to the Amgen Safety department at the same time as reporting to the MHRA and REC.

9.7. Safety reports

The Chief Investigator and KHP-CTO on behalf of the sponsor, will submit a Development Safety Update Report (DSUR) relating to this trial IMP, to the MHRA, REC, Amgen annually.

The Trial Manager will report a list of all SARs (expected and unexpected) and any other safety recommendations to all PIs throughout the course of the trial. This frequency may be reviewed and amended as necessary. This reporting will be done via the Investigator safety report (ISR).

9.8. Contraception and pregnancy

Pregnancy

There are no data from the use of blinatumomab in pregnant women. Blinatumomab should not be used during pregnancy unless the potential benefit outweighs the potential risk to the foetus.

Women of childbearing potential who are sexually active with a non-sterilised male partner, and non-sterilised male patients with a partner of childbearing potential, must use at least one form of effective contraception during and for at least 3 months after treatment with blinatumomab.

A woman is considered of childbearing potential following menarche and until becoming post-menopausal unless:

- Permanently sterile has undergone hysterectomy, bilateral salpingectomy or bilateral oophorectomy.
- Post-menopausal state no menses for 12 months without an alternative medical cause. A high follicle stimulating hormone (FSH) level in the postmenopausal range may be used to confirm a post-menopausal state in women not using hormonal contraception or hormonal replacement therapy.

A man is considered fertile after puberty unless permanently sterile by bilateral orchidectomy. Highly effective forms of contraception are defined as: combined hormonal contraception or progestogen-only hormonal contraception associated with inhibition of ovulation, intrauterine device (IUD), intrauterine hormone-releasing system (IUS), bilateral tubal occlusion, a vasectomised partner, or sexual abstinence.

In case of exposure during pregnancy, depletion of B-cells may be expected in newborns due to the pharmacological properties of the product. Consequently, newborns should be monitored for B-cell depletion and vaccinations with live virus vaccines should be postponed until the infant's B-cell count has recovered.

All pregnancy exposures will be reported to Amgen Safety department within 15 days (within one day if there is concern about potential harm to a pregnant woman or foetus).

Breast-feeding

It is unknown whether blinatumomab or metabolites are excreted in human milk. Based on its pharmacological properties, a risk to the suckling child cannot be excluded. Consequently, as a precautionary measure, breast-feeding is contraindicated during and for at least 48 hours after treatment with blinatumomab.

All potential lactation exposures will be reported to Amgen Safety department within 15 days (within one day if there is concern about potential harm to a nursing mother or infant).

Fertility

No studies have been conducted to evaluate the effects of blinatumomab on fertility. No adverse effects on male or female mouse reproductive organs in 13 week toxicity studies with the murine surrogate molecule

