5.9. Criteria for Treatment Discontinuation

Treatment with blinatumomab will be discontinued in the event of any of the following:

- Haematological or extramedullary relapse
- Confirmed molecular progression between cycles (>1 log rise)
- Investigator's decision that a change of therapy is in the patient's best interest
- Patient or investigator not compliant with the study protocol
- Progression of a medical condition which in the opinion of the investigator should lead to treatment discontinuation
- Administration of relevant non-permitted concomitant medication(s)
- Occurrence of an adverse event which makes discontinuation from treatment desirable or necessary in the investigator's and/or the patient's opinion
- Infusion interruption of more than two weeks due to AE
- Central laboratory determination that the patient's screening bone marrow demonstrates that the patient was ineligible for study treatment due to MRD negativity at the time of enrolment.
- Occurrence of toxicities as described in the Appendix

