6.2. Exclusion Criteria

- 1) 5% or more blasts in the bone marrow or the presence of circulating blasts or current extramedullary involvement by AML.
- 2) History of relevant CNS pathology or current relevant CNS pathology (e.g. seizure, paresis, aphasia, cerebrovascular ischemia/haemorrhage, severe brain injuries, dementia, Parkinson's disease, cerebellar disease, organic brain syndrome, psychosis, coordination or movement disorder).
- 3) Current infiltration of cerebrospinal fluid by AML.
- 4) Body weight under 45kg
- 5) History of or active relevant autoimmune disease.
- 6) Prior allogeneic HSCT within the last 3 months prior to study treatment.
- 7) Systemic cancer chemotherapy within 2 weeks prior to study treatment.
- 8) Radiotherapy within 4 weeks prior to study treatment.
- 9) Treatment with any investigational product within four weeks prior to study treatment.
- 10) Previous treatment with blinatumomab.
- 11) Known hypersensitivity to immunoglobulins or to any other component of the study drug formulation.
- 12) History of malignancy other than AML within five years prior to treatment start with blinatumomab, with the exception of basal cell or squamous cell carcinoma of the skin, or carcinoma "in situ" of the cervix.

- 13) Active infection, any other concurrent disease or medical condition that are deemed to interfere with the conduct of the study as judged by the investigator.
- 14) Nursing women or those with a positive pregnancy test
- 15) Women of childbearing potential (as defined in CTFG guidelines, see appendix) not willing to use a highly effective form of contraception (as defined in CTFG guidelines) during participation in the study and for at least 3 months thereafter, or male patients not willing to ensure use of highly effective contraception during participation in the study and for at least three months thereafter.
- 16) Patients currently enrolled in another interventional clinical trial

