- Coagulation screen
- Serum immunoglobulins (IgG)
- Creatinine clearance (e.g., determined by Cockroft and Gault) will be performed during the screening period to detect any severe kidney function impairment.

- Hepatitis B surface antigen (HBsAg), Hepatitis C virus (HCV) antibody and Human Immuno-deficiency Virus (HIV) testing will be performed during the screening period to exclude an untreated active infection with the respective viruses.

Urinalysis

The presence of glucose, protein and blood in urine will be assessed by dipstick during screening, at D1 prior to the start of infusion at each cycle, and at the End-of-Study visits.

Hepatitis B/C and HIV Testing

Pregnancy Test

A pregnancy test (β -human chorionic gonadotropin [β -HCG] in urine or serum) will be performed at screening in all women of childbearing potential. If at any time during the conduct of the study, a pregnancy is suspected, a pregnancy test should be performed immediately. Tests will be performed by the hospital's local laboratory. If results are positive the patient is ineligible and must be discontinued from study treatment immediately.

Bone marrow biopsy

A bone marrow aspirate, and trephine if necessary, will be performed during the screening period. Patients are potentially eligible for enrolment based on results of RT-qPCR assessment of the screening bone marrow aspirate and one of the following criteria must be fulfilled:

- Two consecutive positive samples with an increase in *RUNX1-RUNX1T1* transcript expression of more than 1 log₁₀ in a patient who previously tested negative in at least two technically adequate samples (molecular relapse)
- Two consecutive positive samples with an increase in *RUNX1-RUNX1T1* transcript expression of more than 1 log₁₀ in a patient who previously tested positive below a level of 500 copies / 10⁵ ABL (molecular progression)
- Two consecutive samples which both test positive at a level above 500 copies / 10⁵ ABL after the completion of primary therapy (molecular persistence of disease).

Concomitant Medication

All concomitant medications will be recorded starting at the first day of screening

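### Sections 7.1.2 and 9.8 give different treatment rules for a patient found pregnant on study, and section 9.8 sets a different contraception requirement from exclusion 15

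*Protocol*

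**What the plan says.** **Treatment once pregnancy is found.** The pregnancy-test paragraph in Protocol section 7.1.2 sits under screening but reaches beyond it: "If at any time during the conduct of the study, a pregnancy is suspected, a pregnancy test should be performed immediately". The consequence follows: "If results are positive the patient is ineligible and must be discontinued from study treatment immediately". Section 9.8, on contraception and pregnancy, has its own sentence: "Blinatumomab should not be used during pregnancy unless the potential benefit outweighs the potential risk to the foetus".

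**Entry.** Inclusion 6 requires a negative test, and exclusion 14 removes "Nursing women or those with a positive pregnancy test". The sections agree at entry, so any conflict arises only after enrolment.

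**Contraception.** Exclusion 15 in section 6.2 removes women of childbearing potential who are "not willing to use a highly effective form of contraception (as defined in CTFG guidelines) during participation in the study". The obligation continues for a minimum of three months once participation ends, and a parallel condition covers male patients. Section 9.8 says that the patients it covers "must use at least one form of effective contraception during and for at least 3 months after treatment with blinatumomab". Further down, after defining childbearing potential and male fertility, 9.8 lists the methods that count as highly effective. It does not say that the method used must come from that list.

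**The concern.** Both treatment passages apply to a participant found pregnant while on blinatumomab. Under 7.1.2 she stops, and nobody has discretion. Under 9.8 the answer depends on weighing benefit against risk. Neither section refers to the other or says which prevails.

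The contraception wording has the same defect. A site that takes its on-study advice from 9.8 would work to a different standard, for a different period and in a different group, from the one applied at entry.

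What is at stake is patient and foetal safety. Section 9.8 itself records that there are no data in pregnant women and that exposed newborns may have depleted B cells. Section 6.8 allows up to two further sites in stage II, so one team's shared understanding cannot be relied on to settle the point.

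**Working it through.** The protocol gives no figure to reproduce, so the check is a comparison of text plus one date calculation.

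**1. Do 7.1.2 and 9.8 cover the same case?** Yes. The test in 7.1.2 is triggered by suspicion at any point in the study, and its consequence concerns study treatment as well as eligibility. Section 9.8 speaks of use in pregnancy generally. A participant who tests positive on treatment falls under both.

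**2. Do they give the same answer?** No. Section 7.1.2 is mandatory and unconditional. Section 9.8 is advisory and carries an exception. Where benefit is judged to outweigh risk, 7.1.2 still requires a stop and 9.8 does not.

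**3. Does another section settle it?** No. The list in 5.9 opens with "Treatment with blinatumomab will be discontinued in the event of any of the following" and does not name pregnancy. Its general entries, such as the investigator's decision, are discretionary. Section 9.8.1 covers reporting and follow-up of a pregnancy, not treatment.

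**4. Contraception, side by side.**

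| | Exclusion 15 (6.2) | Section 9.8 |
|---|---|---|
| Standard | Highly effective | At least one effective form |
| Period | Participation plus at least 3 months | Treatment plus at least 3 months |
| Women | All of childbearing potential | Those sexually active with a non-sterilised male partner |
| Men | Male patients, unqualified | Non-sterilised, with a partner of childbearing potential |

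The two differ in all four rows. The gap for women is smaller in practice than it looks, because the highly effective list in 9.8 includes abstinence and a vasectomised partner. Many women outside the 9.8 group would therefore satisfy exclusion 15 anyway.

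The gap in period depends on what participation means, which exclusion 15 does not define. If it ends with treatment, the two periods coincide. If it includes the efficacy follow-up to 24 months after treatment start (section 5.5), exclusion 15 runs to at least 24 + 3 = 27 months from treatment start.

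**5. How long is the treatment conflict live?** A cycle lasts 6 weeks, or 42 days (section 5.5), and infusion ends on day 29 of a cycle (section 7.2.1).

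- Four cycles on schedule: 3 × 42 + 29 = day 155.
- All three infusion-free intervals between cycles extended by the permitted 7 days: 155 + 3 × 7 = day 176.
- Fewer cycles, for example because of transplant after cycle 1, end it sooner. Interruptions for toxicity can end it later.

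The schedule of events places pregnancy tests at screening, at the 90-day visit and at any withdrawal visit. During treatment, therefore, a pregnancy is normally found through the suspicion-triggered test in 7.1.2, and that is the result on which 7.1.2 and 9.8 diverge.

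**6. Does it reach the statistics?** No. The primary endpoint is read from the day 29 marrow of cycle 1 (section 8.2), and section 5.5 keeps that assessment for patients who stop during cycle 1. The two-stage boundaries do not depend on the pregnancy wording.

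**The case against.** The best defence is that 7.1.2 is the only specific instruction for a positive test, while the sentence in 9.8 is general product information. It sits beside text on newborn B cells, breast-feeding and mouse fertility, and it names no test result, decision-maker or restart procedure. On that view the specific rule governs. Likewise, every enrolled patient to whom exclusion 15 applies has already accepted the stricter contraception standard, and the list of highly effective methods in 9.8 suggests that a word was dropped from its requirement.

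This explains how the text may have arisen. It does not remove the conflict: 9.8 is operative protocol text, its contraception sentence is framed as an obligation, and nothing makes 9.8 subordinate to 7.1.2 or 6.2.

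The defence does succeed against several stronger readings that a reader might infer:

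- **That 9.8 allows a stopped patient to be dosed again.** It says nothing about restarting after a positive test.
- **That 5.9 is a third contradiction.** Its list is not stated to be exhaustive, and 7.1.2 can require a stop without being repeated there.
- **That the protocol names a method that passes 9.8 and fails exclusion 15.** The only methods 9.8 lists are the highly effective ones. The mismatch is between standards, not between named methods.
- **That the treatment conflict lasts until the 90-day visit**, near day 155 + 90 = 245. Once the last infusion has ended there is no treatment to stop or continue. Sparse scheduled testing is a separate matter and is not evidence of contradiction.

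**Conclusion.** The point holds as an internal inconsistency in two places. First, a positive pregnancy test on study leads to an unconditional stop under 7.1.2 and to a conditional position under 9.8. Second, exclusion 15 and 9.8 differ on the contraception standard and the population, and on the period unless participation is taken to end with treatment.

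Its reach is limited. The treatment conflict applies while infusion is running or more cycles are planned: to about day 155 with four cycles on schedule, or about day 176 with every between-cycle interval fully extended, assuming no interruptions for toxicity. It concerns women of childbearing potential among the 17 patients, a number the protocol does not give and which may be small. The contraception mismatch also affects male patients and extends beyond the end of treatment.

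Nothing here changes the sample size, the error rates or the primary analysis. The case for correction rests on patient and foetal safety and on sites being able to follow one instruction. No view is taken on which clinical rule is right.

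**What to change.** - Reconcile 7.1.2 and 9.8 so that a single rule for study treatment after a positive pregnancy test appears in both, or appears in one and is cross-referenced from the other.
- Reconcile exclusion 15 in 6.2 with 9.8 so that one contraception standard, one period and one population apply to women and to men. Tie the list of methods in 9.8 explicitly to that requirement, and say when participation ends for this purpose.
- A cross-reference to pregnancy in 5.9 would help sites but is optional.

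The sponsor and clinical team should decide the content of each rule. The cost is protocol wording, with a check that the participant information sheet says the same. No design element, visit or analysis changes.
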